3. STUDY DESIGN

This is a Phase II, randomized, double-blind, placebo-controlled study to assess 2 dose levels of GLS-1027 for the prevention of treatment failure among participants admitted to hospital with PCR confirmed infection with SARS-CoV-2 (WHO classification 3 or 4). The enrollment period will extend to 72 hours from hospital admission.

Participants will be randomized to placebo or GLS-1027 at either 120 mg or 360 mg daily in a 1:1:1 ratio as adjunctive to standard of care based on the hospital COVID-19 treatment algorithm and/or local COVID-19 treatment practices. Participants will be administered study drug for a maximum treatment period of 28 days or until discharge or death, whichever comes first. Follow-up will continue through to Day 56 to document AEs and outcome as to discharge, death, or WHO COVID-19 classification level if subject remains hospitalized.

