3.2 Data and Safety Monitoring Board (DSMB)

In addition to internal monitoring of safety data by the site PI and medical monitor, an independent data and safety monitoring board (DSMB), consisting of expert members not related to the clinical trial or sponsor staff will provide safety oversight. The DSMB will include at a minimum three members: a physician specializing in either Infectious Disease or Pulmonary / Critical Care, a second health-care practitioner who may be a physician, and someone with statistical experience (physician or non-physician).

The DSMB will meet at the start of the clinical trial to review and finalize the DSMB charter. At a minimum, the DSMB will meet to review interim data when 50% of the target enrollees (66 subjects) have completed the primary observation period to discharge, death, discontinuation or 28 days of treatment. The DSMB will review safety data and outcomes for enrolled subjects in a blinded manner. Unless a safety signal has been encountered, enrollment will continue through to at least 44 per group (total N=132).

A summary of all AEs and SAEs will be provided to the DSMB as masked treatment groups by an independent statistician together with a summary rates of retention in the study, and other relevant events. Reports will include a summary of participants' baseline characteristics, early study discontinuations, and a summary of participants who reach primary endpoint and/or end of study follow-up. The DSMB may recommend corrective measures, up to termination of the study for safety concerns. Study termination can be implemented by the Project PI, FDA, Sponsor, or site-specific or other supervising IRBs. Conference call or video conference meetings are allowed as necessary.

Additional details can be found in the DSMB Charter.

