5.2 Packaging and Labeling

GLS-1027 will be supplied to the investigational pharmacy in bottles of 50 capsules, while the placebo will be supplied in bottles of 100 capsules. Drug will be dispensed by pharmacy personnel to study participants as part of daily medication dispensing to maintain blinding of other study personnel.

Drug product vial label is shown below in Table 5.2-1.

GLS-1027	PLACEBO
GLS-1027 Capsules, 120 mg	Placebo Capsules, 105 mg
Protocol No. GLS27-005	Protocol No. GLS27-005
Lot No. xxxx	Lot No. xxxx
Quantity: 50 capsules	Quantity: 100 capsules
(Caution New Drug Limited by Federal (United States)	(Caution New Drug Limited by Federal (United States)
Law to Investigational Use	Law to Investigational Use
Keep out of reach from children: Take as directed	Keep out of reach from children: Take as directed
Store at 25°C (77°F) excursion permitted to 15°-30°C	Store at 25°C (77°F) excursion permitted to 15°-30°C
(56° - 86°F)	(56° - 86°F)
Sponsor: GeneOne Life Science	Sponsor: GeneOne Life Science
Mfd by CoreRx Inc., [name],	Mfd by CoreRx Inc., [name],
[name]	[name]

Table 5.2-1. GLS-1027 and Placebo drug product vial labels

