7.3.2 Reasons to Discontinue Treatment

Discontinuation or interruption of study drug

Study drug will be discontinued with any of the following:

- 1. Diagnosis of pregnancy.
- 2. Anaphylaxis or allergic reaction possibly related to study drug

Study drug will be temporarily halted with any of the following:

- 3. If the eGFR falls below 60 mL/min/1.73 m²
- 4. If the patient is intubated and/or ECMO is initiated
- 5. If oral administration is not possible
- 6. For those with baseline serum bilirubin in the normal range: a serum bilirubin ≥ 5 times the upper limit of normal (ULN)
- For those with baseline serum bilirubin above the normal range: a serum bilirubin ≥ 10 times the ULN

- 8. Transaminase (ALT or AST) elevation of \geq 20 times the ULN
- 9. An absolute neutrophil count of < 1000 (Grade 4)
- 10. Electrocardiographic findings of any of the following: Torsades de Pointes, polymorphic ventricular tachycardia
- 11. Malignant hypertension characterized by a systolic BP of ≥ 220 mm Hg or a diastolic BP

≥ 110 mm Hg with concomitant neurologic deficit or need for urgent medical intervention

- 12. Headache with neurologic deficit in a patient without history of migraine or similar syndrome or condition
- 13. Gastric hemorrhage requiring transfusion or other emergent intervention
- 14. Uncontrolled emesis for greater than 24 hours, or incident emesis considered to be definitely or probably caused by study drug
- 15. Occurrence of any opportunistic infection

Study drug should be reinstituted when the event that resulted in temporary interruption of study drug administration has resolved or has improved to a Grade 2 event or lower. In the case that the subject has been intubated or started on ECMO, study drug should be restarted once extubated and/or ECMO discontinued and oral administration of medications is possible. Exceptions are any diagnosis of pregnancy or an opportunistic infection. If a second episode of the same adverse event occurs, study drug will be stopped and not restarted.

If two or more episodes of anaphylaxis possibly related to study drug occur, then the unblinded clinical research coordinator will request that pharmacy provide a report regarding study drug assignments of these participants to the DSMB to determine potential causality. The DSMB will review and determine appropriateness of study continuation.

All episodes of study drug interruption or stoppage should be reported to the Medical Monitor.

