7.3.3 Unblinding

This is a double-blind study. Treatment assignments should be maintained as blinded unless such unblinding is considered as critical to the care and well-being of the subject. Unblinding should occur following discussion with the Sponsor Medical Monitor, however, emergency unblinding can occur if the Investigator deems that such a delay would unduly harm the subject and knowledge of the treatment assignment is a critical factor in medical decision making versus a discontinuation of study drug until discussion with the Medical Monitor. In the case of unblinding, the Investigator must record the date, time and reason for unblinding, however, the Investigator is not required to inform the Sponsor of treatment assignment. Unblinded treatment assignment will only be accessible to those who require such information as part of medical decision making and for those involved in Safety reporting to Health Authorities and/or the relevant IRB.

The Investigational Pharmacy will maintain a listing of subject treatment assignments and will provide a mechanism for unblinding in emergency situations.

8. STATISTICAL METHODS and CONSIDERATIONS

Prior to unblinding and analysis of the final study data, a detailed Statistical Analysis Plan (SAP) will be written describing all analyses that will be performed for reporting of results from this clinical trial.

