5. GENERAL ANALYSIS CONSIDERATIONS

The statistical analysis results will be reported using tables, listings, and figures (TLFs). Summaries of continuous variables will display means, standard deviations (SDs), medians, minimums, maximums, and the number of observations. Summaries of categorical variables will display frequency counts and percentages.

CONFIDENTIAL Page 8 03DEC2021

^h Record maximal daily level of PEEP and delivered FiO2 by mechanical ventilation, if participant is receiving mechanical ventilation

All analyses will be performed using SAS® Version 9.4 or higher.

A masked interim analysis will be performed when 22 subjects in each group have been assessed for the primary endpoint of treatment failure. The primary goals of this analysis are to review blinded safety to ensure that GLS-1027 has no concerns or causes worsening conditions. Unless safety is of concern, the study will not be stopped for futility and enrollment will continue to the targeted sample size of 132.

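### The DSMB reviews safety and outcomes only as masked groups, with no stated way to learn which arm is which, so between-arm contrasts alone cannot show the direction of an imbalance

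*Protocol*

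**What the plan says.** Protocol 3 sets up three arms: "Participants will be randomized to placebo or GLS-1027 at either 120 mg or 360 mg daily in a 1:1:1 ratio".

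Protocol 3.2 has the board work under the blind: "The DSMB will review safety data and outcomes for enrolled subjects in a blinded manner". The form of the report is also fixed: "A summary of all AEs and SAEs will be provided to the DSMB as masked treatment groups by an independent statistician". The board may recommend corrective measures up to termination, and the part of 7.3.2 on pausing the trial lets it recommend a global pause after a safety signal. Protocol 3.2 then refers elsewhere for the rest: "Additional details can be found in the DSMB Charter". That charter is not among the documents.

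The synopsis and Protocol 8.8 call the interim masked, at 22 subjects per group. SAP 5 repeats this and gives the purpose: "The primary goals of this analysis are to review blinded safety to ensure that GLS-1027 has no concerns or causes worsening conditions".

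One sentence sends assignments to the board. If two or more possibly related anaphylaxis episodes occur, Protocol 7.3.2 says "then the unblinded clinical research coordinator will request that pharmacy provide a report regarding study drug assignments of these participants to the DSMB". This covers the affected participants, not the arms.

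Two other sections bear on who may know assignments. Protocol 5.2 has pharmacy staff dispense "to maintain blinding of other study personnel". Protocol 7.3.3 says "Unblinded treatment assignment will only be accessible to those who require such information as part of medical decision making", and adds those who report safety to health authorities or the IRB. It also gives the investigator an emergency route for a single subject.

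**The concern.** The stated purpose of the interim is directional: is GLS-1027 making patients worse? Masked labels show that groups differ, but not which of them is placebo. In a three-arm trial with one placebo, a table with one bad group and two good ones is expected if both doses work, because placebo is the outlier. It is also expected if one dose harms, because that dose is the outlier. Death and intubation count in both the efficacy and the safety picture, so the outcome data do not resolve the ambiguity.

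A board that cannot read the direction could let a harmful dose continue, or recommend a pause because placebo patients are doing badly. Incidence of SAEs is itself a primary outcome.

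A smaller point concerns the unblinded coordinator in 7.3.2. The role appears nowhere else and is not among those to whom 7.3.3 gives access.

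**Working it through.** **Inputs.** Three arms, 1:1:1 (Protocol 3). Interim at 22 per arm, 66 in total (Protocol 3.2 and 8.8; SAP 5). Planned failure rates of 50% on placebo and 25% on either dose (Protocol 8.2). The documents give no rate for a harm scenario. As an assumption, harm means one dose 25 points above placebo (the planned effect reversed) and the other dose equal to placebo, with the placebo rate p varied from 25% to 50%.

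**The plan's own figure.** The plan states no operating characteristic for the masked review. The figure attached to these rates is 70% power at 44 per group. The standard error is √[(0.5×0.5 + 0.25×0.75)/44] = √(0.4375/44) = 0.0997, so the standardized effect is 0.25/0.0997 = 2.507. A two-look O'Brien-Fleming z-test with bounds 2.797 and 1.977 gives 70.4%. The 70% reproduces, so 50% and 25% are the right planning inputs. (The Fisher test that the plan names gives 61.1% at 44 per group. That is a separate matter.)

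**Expected counts at the interim.** 22 × 0.50 = 11 and 22 × 0.25 = 5.5. If both doses work, the groups expect 11, 5.5 and 5.5 failures. If one dose harms from a 25% placebo rate, they also expect 11, 5.5 and 5.5.

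**Label symmetry.** With labels unknown, the likelihood of counts (x₁, x₂, x₃) averages over which group is the outlier:

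L = (1/3) Σⱼ Bin(xⱼ; 22, a) × Π_{k≠j} Bin(x_k; 22, b).

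Placebo a with both doses at b gives this L. So does placebo b with one dose at a and the other at b. The likelihood ratio is 1 for every possible table, whatever a and b are. With a = 50% and b = 25%, any classifier is wrong half the time. In the same way, one effective dose (placebo 50, doses 50 and 25) cannot be told from harm at both (placebo 25, doses 50 and 50).

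**What the absolute level adds.** The best classifier was told both candidate sets of rates and asked to choose between benefit at both doses (50/25/25) and harm at one dose (p, p+25, p). There were 100,000 simulated interims per scenario.

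| Placebo rate p under harm | Harm read as benefit | Benefit read as harm |
|---|---|---|
| 25% | 50% | 50% |
| 30% | 33.3% | 32.5% |
| 35% | 20.1% | 18.3% |
| 40% | 9.4% | 10.3% |
| 50% | 2.1% | 1.2% |

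These are best-case errors. A board that does not know the rates can do no better on average.

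**What labels would add.** Even with arms identified, a two-sided Fisher test of 50% against 25% at 22 per arm has 28.5% power. Opening the codes supplies direction, not power.

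**The coordinator.** Section 5.2 aims to keep staff outside pharmacy blinded. Section 7.3.3 limits access to two categories and names neither a coordinator nor the DSMB. Section 7.3.2 assumes that an unblinded coordinator exists and that the DSMB receives some assignments. The three sections do not describe the same access rules.

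**The case against.** The strongest objection is that the DSMB sees levels as well as contrasts. On the plan's own 50% placebo rate, a 25-point harm at one dose would give 50/50/75, which looks nothing like 50/25/25 and would be misread only 1-2% of the time. Protocol 1.1 even says that progression is likely above 50%. This stands, and it rules out the reading that the board cannot tell harm from benefit at all. That reading is true only of between-arm contrasts.

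The 50% is, however, a weak anchor. Protocol 8.2 applies it to progression to level 6 or above and says that the rate of salvage therapy is unknown. SAP 4 applies the same 50% to a wider endpoint that adds high-flow oxygen, non-invasive ventilation and any non-study immune modulator. Protocol 1.1 ties it to patients on supplemental oxygen, whereas level 3 patients, who need none, are eligible. For SAEs there is no expected rate to use as an anchor.

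The charter may hold an unmasking rule, and no sentence forbids the board to ask for the codes. Both are fair, and the charter cannot be checked. But 3.2 states blinded review without exception, so a charter that allowed unmasking would conflict with it.

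A reader might also infer that 7.3.2 is the only unmasking route in the trial. It is not, because 7.3.3 has the single-subject emergency route. Section 7.3.2 is the only stated route to the DSMB.

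Nor do the documents show that the blinding rules prohibit the coordinator or that the role biases the endpoint. No sentence forbids it, the coordinator only requests a report that pharmacy supplies, and nothing says that this person starts salvage drugs or stops study drug.

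**Conclusion.** The point holds in limited form. As written, the DSMB's safety review rests on masked groups, and the available text gives it no access to arm identity. Contrasts between the three groups therefore cannot give the direction of an imbalance, although direction is what SAP 5 asks of the review. For treatment failure, the chance of misreading a 25-point harm at one dose as benefit at both, or the reverse, runs from 50% when the rates mirror each other down to 1-2% if the placebo rate is 50%. These figures rest on the assumed harm scenario and on a classifier given the true candidate rates. For SAEs the ambiguity has no stated bound.

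The documents do not show that the board is unable to detect harm, or that no unmasking rule exists anywhere. The change is worth making because it is cheap and bears on patient safety. The coordinator is a wording inconsistency to be reconciled, and no breach of the blind is shown.

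**What to change.** Amend Protocol 3.2 and 8.8, the matching synopsis text and SAP 5, and align the DSMB charter. The independent statistician who already prepares the reports should hold the arm codes. The DSMB may open them at its own request when it sees a between-group imbalance in deaths, SAEs or outcomes. Sponsor, sites and medical monitor stay blinded. Add the DSMB and this statistician to the access list in 7.3.3.

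State also that nobody with access to the unmasked report takes part in any decision to increase enrollment. Section 7.3.2 leaves such an increase open, and 3.2 and 8.8 treat 44 per group, or 132 in total, as a minimum. The plan provides for stopping only on safety grounds, so access for safety review adds no efficacy test and needs no change to alpha.

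Separately, reconcile the unblinded coordinator in 7.3.2 with 5.2 and 7.3.3, for example by routing the request to pharmacy through the independent statistician.

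The cost is wording in the protocol, SAP and charter, plus a firewall around the unmasked report. No new body, data or sample size is needed.

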4. SELECTION AND ENROLLMENT OF PARTICIPANTS

4.1 Recruitment of Participants

4.2 Inclusion Criteria for enrollment

- 1. Age 18 years or older
- 2. Able to provide informed consent
- 3. Able and willing to comply with study procedures
- 4. Enrollment within 72 hrs of hospitalization with a diagnosis of PCR confirmed SARS-CoV-2 infection
- 5. WHO COVID-19 classification level of 3 or 4

4.3 Exclusion Criteria for enrollment

- 1. Pregnant or lactating
- 2. SpO2 less than 90% on room air or less than 95% on supplemental oxygen
- 3. Calculated GFR < 60 (Cockcroft-Gault)
- 4. Meets hospital treatment algorithm for treatment with dexamethasone at a dose of 6 mg/day for a 10 day course. A single bolus dose of 6 mg of dexamethasone given in the

Emergency Department and continued at a dose of \leq 3.5 mg/day or less is allowed.

- 5. Meets treatment algorithm criteria for treatment with toclizumab or other anti-IL-6 agent
- 6. Treatment with an anti-IL-6 inhibitor, anti-IL-1 inhibitor, anti-TNF monoclonal antibody, or anti-JAK inhibitor (see Appendix A for exclusionary period for individual drugs)
- 7. Participation in a COVID-19 clinical trial that includes prescription of a drug with anticytokine activity
- 8. Treatment within the past 60 days with a chemotherapeutic agent
- Current outpatient treatment with systemic corticosteroids at a dose equivalent of 20 mg/day or greater of prednisone or prednisolone, 16 mg/day or greater of methylprednisolone
- 10. Diagnosis of leukemia or lymphoma
- 11. WHO COVID-19 classification level of 5 or greater (use of high-flow oxygen, nonmechanical ventilation such as CPAP, mechanical ventilation)

4.4 Discontinuation/Withdrawal of Study Participants

The Informed Consent will require that subjects allow follow-up for the primary outcome and safety through to 56 days post-enrollment or death. A subject may withdraw from the study by withdrawing consent to continue participation. If a subject withdraws consent from participating in the study at any time after enrollment, but prior to the final scheduled study visit, the investigator will make every effort to have the participant complete all assessments at the time of withdrawal. All data collected up to the time of withdrawal will be used for data analyses. The request to withdraw consent must be documented.

Discontinuing treatment is not a reason for withdrawing from participating in the study. Subjects who discontinue treatment for any reason should be followed until 56 days postenrollment or death, whichever comes first.

Reasons for treatment discontinuation are defined below.

- The PI or Medical Monitor consider that continuation of treatment may pose a safety risk to the subject. Treatment discontinuation will be considered a treatment failure, unless the subject discontinues treatment due to pregnancy or renal insufficiency. The subject should however continue to be monitored as per protocol for outcome measures through to study end (Day 56).
- Adverse event (Adverse Reaction): clinical or laboratory events that in the medical judgement of the investigator are grounds for discontinuation of treatment. This will be considered as a treatment failure. Subjects should however continue to be monitored as per protocol for outcome measures through to study end (Day 56).
- Lost to follow-up: for subjects who are discharged from the hospital within 28 days of treatment initiation who cannot be contacted after multiple attempts, will be

considered as Lost to Follow-up for purposes of Long-term outcomes (56 days). Otherwise, without relapse of COVID-19 symptoms, discharge within 28 days of enrollment is considered a treatment success. For subjects who are discharged from the hospital, every effort should be made to contact the subject to determine clinical status and adverse events post-discharge.

• Transfer of subject to another hospital. All transfers will be considered treatment failures.

4.5 Treatment with dexamethasone post-enrollment

Treatment with dexamethasone at a dose of 6 mg/day for 10 days is currently considered as part of the standard of care for COVID-19 at many institutions, however, the specifics of treatment and whether such treatment is formally algorithm based varies between institutions. Moreover, it is recognized that dexamethasone treatment may be ordered as part of clinical care for some subjects after enrollment into the study.

Enrollment into the study is allowed for individuals who have not been treated with dexamethasone since hospital admission. Enrollment into the study is also allowed for those have received a single bolus dose of 6 mg of dexamethasone at presentation to the hospital with or without continuation of dexamethasone at a dose of 3.5 mg/day or less.

Enrolled subjects for whom dexamethasone is initiated within 72 hours of the time of 1st dose of study drug will be considered to have required dexamethasone at the time of presentation to hospital and will be treated the same as those who received a single bolus dose of 6 mg at presentation to the hospital. Unless dexamethasone is prescribed for 10 days at 6 mg, sSuch subjects will not be considered to have met the definition of the need for salvage therapy, and will not be considered as meeting a study endpoint for failure.

Enrolled subjects for whom dexamethasone is ordered at a dose of ≥ 6 mg per day and is initiated 72 hours or later after the 1st dose of study drug will be considered to have met the definition of need for salvage therapy and thus have met a study endpoint for failure. Initiation of treatment with dexamethasone at a dose of less than 6 mg/day after enrollment in the study will not be considered as treatment failure.

Subjects will be subgrouped for summary by concomitant bolus dexamethasone within 72 hours of enrollment versus no concomitant dexamethasone with 72 hours of enrollment.

